8.11.4.2.4 SAEs within 6 months post-vaccination

The number of subjects, number of events, and percentage of SAEs occurring within 6 months post-vaccination in each group will be summarized. The number of subjects, number of events, and percentage of SAEs occurring within 6 months post-vaccination in each group will be summarized by severity and symptom. The inter-group comparison is performed using chi-square test or Fisher's exact test.

8.11.4.3 Immunogenicity analysis

8.11.4.3.1 Geometric mean titer (GMT) of anti-SARS-CoV-2 specific neutralizing antibodies in subjects in the immunogenicity group at 14 days, 28 days, 3 months, and 6 months after booster immunization

The GMT in each group at each visit will be summarized using number of subjects, geometric mean, standard deviation, median, quartile, maximum, minimum, and 95% CI, etc. Inter-group differences will be compared using a t test. The reverse cumulative distribution is plotted. The analysis of GMC of anti-SARS-CoV-2 S-RBD IgG antibodies will be stratified by baseline anti- Ad5 neutralizing antibody titer and age.

The GMI in each group will be summarized using number of subjects, geometric mean, standard deviation, median, quartiles, maximum, minimum, and 95% CI, etc. Inter-group differences will be compared using a t test. The GMI of anti-SARS-CoV-2 S-RBD IgG antibodies will be compared between the two routes of administration, stratified by baseline anti-Ad5 neutralizing antibody titer and age.

The seroconversion rate of each group is summarized and indicated using number of subjects and percentages to calculate the 95% CI of seroconversion rate. Inter-group differences will be compared using chi-square test or Fisher's exact test. The seroconversion rates of anti-SARS-CoV-2 S-RBD IgG antibodies between the two routes of administration will be compared, stratified by baseline anti-Ad5 neutralizing antibody titer.

8.11.4.3.2 GMC, GMI, and seroconversion rate of anti-SARS-CoV-2 RBD protein IgG antibodies in subjects in the immunogenicity group at 14 days, 28 days, 3 months, and 6 months after immunization;

The GMC in each group at each visit will be summarized using number of subjects, geometric mean, standard deviation, median, quartile, maximum, minimum, and 95% CI, etc. Inter-group differences will be compared using a t test. The reverse cumulative distribution is plotted. The analysis of GMC of anti-SARS-CoV-2 S-RBD IgG antibodies will be stratified by baseline anti-Ad5 neutralizing antibody titer and age.

The GMI in each group will be summarized using number of subjects, geometric mean, standard deviation, median, quartiles, maximum, minimum, and 95% CI, etc. Inter-group differences will be compared using a t test. The GMI of anti-SARS-CoV-2 S-RBD IgG antibodies between the two routes of administration will be compared, stratified by baseline anti-Ad5 neutralizing antibody titer and age.

The seroconversion rate of each group is summarized and indicated using number of subjects and percentages to calculate the 95% CI of seroconversion rate. Inter-group differences will be compared using chi-square test or Fisher's exact test. The seroconversion rate of anti-SARS-CoV-2 S-RBD IgG antibodies between the two routes of administration will be compared, stratified by baseline anti-Ad5 neutralizing antibody titer.

8.11.4.3.3 GMT, seroconversion rate, and GMI of certain VOC/VOI cross-neutralizing antibodies in subjects in the immunogenicity group at 28 days after booster immunization

The geometric mean titer (GMT) of each group at each visit are summarized and described using number of subjects, geometric mean, standard deviation, median, quartiles, maximum, minimum values, etc. Inter-group differences will be compared using a t test. The reverse cumulative distribution is plotted. The analysis of GMT of VOC/VOI cross-neutralizing antibodies will be stratified by baseline anti-Ad5 neutralizing antibody titer and age.

The seroconversion rate of each group is summarized and indicated using number of subjects and percentages to calculate the 95% CI of seroconversion rate. Inter-group differences will be compared using chi-square test or Fisher's exact test. The GMI in each group will be summarized using number of subjects, geometric mean, standard deviation, median, quartiles, maximum, minimum, and 95% CI, etc. Inter-group differences will be compared using a t test.

8.11.4.3.4 GMC, seroconversion rate, and GMI of salivary sIgA antibodies in subjects in the immunogenicity group at 14 days, 3 months, and 6 months after immunization

The GMC in each group at each visit will be summarized using number of subjects, geometric mean, standard deviation, median, quartile, maximum, minimum, and 95% CI, etc. Inter-group differences will be compared using a t test. The reverse cumulative distribution is plotted.

The GMI in each group at each visit will be summarized using number of subjects, geometric mean, standard deviation, median, quartiles, maximum, minimum, and 95% CI, etc. Inter-group differences will be compared using a t test.

The seroconversion rate of each group in each visit is summarized and indicated using number of subjects and percentages to calculate the 95% CI of seroconversion rate. Inter- group differences will be compared using chi-square test or Fisher's exact test.

8.11.4.3.5 GMC, seroconversion rate, and GMI of serum IgA antibodies in subjects in the immunogenicity group at 14 days, 3 months, and 6 months after immunization

The GMC in each group at each visit will be summarized using number of subjects, geometric mean, standard deviation, median, quartile, maximum, minimum, and 95% CI, etc. Inter-group differences will be compared using a t test. The reverse cumulative distribution is plotted.

The GMI in each group at each visit will be summarized using number of subjects, geometric mean, standard deviation, median, quartiles, maximum, minimum, and 95% CI, etc. Inter-group differences will be compared using a t test.

The seroconversion rate of each group in each visit is summarized and indicated using number of subjects and percentages to calculate the 95% CI of seroconversion rate. Inter- group differences will be compared using chi-square test or Fisher's exact test.

Stratified by baseline anti-Ad5 neutralizing antibody titer and age.

8.11.4.3.6 Seropositive rate and response levels of IFN- γ , TNF- α , IL-2, IL-4, IL-5 and IL-13 in CD4⁺ and CD8⁺ T cells in subjects in the immunogenicity group at 14 days after immunization

The response levels in each group at each visit will be summarized using number of subjects, geometric mean, standard deviation, median, quartile, maximum, minimum, and 95% CI, etc. Inter-group differences will be compared using a t test.

The seroconversion rate in each group at each visit will be summarized by number and percentage of subjects, and the 95% CI will be calculated. Inter-group differences will be compared using chi- square test or Fisher's exact test.

Refer to the Statistical Analysis Plan (SAP) for details.

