6.2 Sample Size Estimation

This study includes a safety group and an immunogenicity group. The immunogenicity group also includes a cellular immunity group. Approximately 10,000 subjects are planned to be enrolled in the safety group. This sample size provides at least 85% power to detect 1 case of adverse reaction in the investigational vaccine group with an incidence of 0.02% (assuming that the background incidence of a given adverse event is 1 in a million).

Rationale for sample size determination in the immunogenicity group: Based on data from preliminary clinical studies (Project No.: JSVCT127), the GMT of anti-SARS-CoV-2 neutralizing antibodies at 28 days after administering a booster dose of the inactivated vaccine in the control group was around 16. The GMT, standard deviation, of anti-SARS-CoV-2 neutralizing antibodies at 28 days after immunization in the investigational vaccine group were 32, and 9, respectively. Using PASS 15.0 procedure of Two-Sample T-Tests Assuming Equal Variance, 183 subjects in each of the investigational vaccine group and the control group (1:1 ratio) will be required for a one-sided $\alpha = 0.025$ test with at least 85% power to demonstrate that the antibody titer after booster dose in the investigational vaccine group is superior to the control group. Considering the dropout of the study, 420 subjects will be enrolled in the immunogenicity subgroup. The cellular immunity group will consist of the first 60 subjects in the immunogenicity group of a single site managed by Jiangsu CDC.

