6.3.2 Randomization numbering rules

Before vaccination during V1, each subject is assigned a unique randomization number by the study personnel on site via the IWRS system according to their enrollment sequence. Each randomization number corresponds to only one subject until the end of the study.

This study intends to enroll 10420 subjects aged 18 years and above, of which the population aged 60 years and above accounts for approximately $\geq 30\%$. A total of 6 study centers will be established (each study site may set up multiple vaccination sites). The 420 subjects in the immunogenicity group will be randomized to receive a booster dose of Ad5-nCoV-IH or inactivated SARS-CoV-2 vaccine in a 1:1 ratio. Rule for randomization numbers: Site number + 4-digit serial number, each site number will start with 0001. Jiangsu CDC + 0001–0060 will also be included in the cellular immunity subgroup. In the case of a subject dropping out after randomization but before vaccination, a substitute may be randomized. For example, if subject 0001 drops out before vaccination, the next enrolled subject will be the substitute with a randomization number of 10001; if the substitute also drops out before vaccination, the next enrolled subject will be a substitute with a randomization number of 20001; 9 substitutes is the maximum.

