8.8.7 VOC/VOI cross-neutralization testing

The levels of cross-neutralizing antibodies to VOC/COI will be tested in subjects in the immunogenicity group before and 28 days after booster immunization to compare the protective effects of the two vaccines on VOC and VOI.

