8.11.3 Selection of analysis sets

Safety set (SS): All randomized subjects who receive the immunization will be included in the safety evaluation. Data in violation of the protocol were not rejected.

Immunogenicity evaluation datasets:

Full analysis set (FAS): FAS included an ideal subject population determined by the intention-to-treat (ITT) principles. All subjects enrolled and vaccinated were included in the FAS, whether or not they had positive baseline antibody levels or major deviation from the protocol.

Per protocol set (PPS): PPS is a subset of FAS; the subjects in this dataset are more compliant with the protocol, have no major protocol violations during the study, and meet all eligibility criteria.

PPS will be used as the primary analysis dataset for immunogenicity analysis in this trial. However, FAS will be analyzed as well. Any inconsistencies between the FAS and PPS results will be discussed in the report.

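### The primary GMT comparison is a valid but unadjusted t test that leaves the measured pre-booster titer, age group and centre unused; a prespecified ANCOVA would gain precision at almost no cost

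*Protocol*

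**What the plan says.** The primary immunogenicity endpoint is the day-28 GMT against omicron BA.4/5 (Protocol 6.1.1). Superiority requires the one-sided 97.5% lower limit of the GMT ratio to exceed 1 (8.11.2). For neutralizing GMTs, section 8.11.4.3.1 says: "Inter-group differences will be compared using a t test". Section 8.11.4.3.3, on variant cross-neutralization, names the same test, so the method is a t test whichever section governs BA.4/5. The sample size assumes it too: "Using PASS 15.0 procedure of Two-Sample T-Tests Assuming Equal Variance" (6.2).

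The trial also collects the following:
- **Pre-booster neutralizing titer.** It is measured in the whole immunogenicity group (8.8.2, no strain named). Variant titers "will be tested in subjects in the immunogenicity group before and 28 days after booster immunization" (8.8.7, variants not listed).
- **Age group.** Superiority within 18-59 and 60 or over is tested as supportive evidence after the overall test (8.11.2).
- **Centre.** Six centres have fixed quotas (Synopsis, Table 1). Randomization numbers follow the rule "Site number + 4-digit serial number, each site number will start with 0001" (6.3.2). The analysis sections do not mention centre.

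On the analysis set, 8.11.3 states: "PPS will be used as the primary analysis dataset for immunogenicity analysis in this trial". The FAS is analysed as well, and any disagreement is to be discussed in the report.

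**The concern.** The pre-booster titer is a natural predictor of the post-booster titer. When such a predictor is measured in every subject and left out of the model, the variance it explains stays in the error term. The interval for the GMT ratio is then wider than it need be, and a chance baseline difference between arms passes straight into the estimate. What is at stake is precision and robustness to imbalance, not the validity of the test.

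A separate and secondary matter is the analysis set. Section 7.5 lets subjects fall out of the PPS on grounds that arise after randomization, including too much missing information, with no threshold given. The trial is open-label, so such judgements can be made with allocation known. For a superiority claim, the set closest to randomization is the better base.

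**Working it through.** **Inputs (Protocol 6.2).** Control: "a booster dose of the inactivated vaccine in the control group was around 16". Test arm GMT and SD: "in the investigational vaccine group were 32, and 9, respectively". Error rates: "will be required for a one-sided $\alpha = 0.025$ test with at least 85% power". Stated size: 183 per arm, 1:1.

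**Step 1: reproduce the plan.** On the log scale the difference is ln(32/16) = 0.693. The SD of 9 reproduces the stated size only as a geometric SD, that is a log SD of ln 9 = 2.197. Read on the raw titer scale (difference 16, SD 9), it would need only 6 to 7 per arm.

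- Standardized effect d = 0.693/2.197 = 0.3155.
- Required n per arm for 85% power: 181 (normal) or 182 (exact t), against 183 stated.
- Power at 183 per arm: noncentrality = 0.3155 × sqrt(183/2) = 3.02, giving 85.5% (normal) or 85.3% (exact t).

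The stated figure reproduces, and it rests on the unadjusted test.

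**Step 2: effect of adjustment.** With baseline in the model, the residual SD is 2.197 × sqrt(1 − r²), so d becomes 0.3155/sqrt(1 − r²). The CI width on the log scale is multiplied by sqrt(1 − r²), and the equivalent sample size by 1/(1 − r²). Here r is the within-arm correlation of baseline and day-28 log titers, or the multiple correlation if age and centre are included. The documents do not give it, so the range is an assumption. The few degrees of freedom used by the covariates are ignored, which is immaterial with 366 subjects.

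| r (assumed) | Power at 183 per arm | n per arm for 85% | CI narrower by | Equivalent extra subjects |
|---|---|---|---|---|
| 0 | 85.3% | 182 | 0% | 0% |
| 0.1 | 85.7% | 180 | 0.5% | 1% |
| 0.2 | 86.7% | 175 | 2% | 4% |
| 0.3 | 88.4% | 166 | 5% | 10% |
| 0.5 | 93.5% | 137 | 13% | 33% |
| 0.6 | 96.4% | 117 | 20% | 56% |

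**Step 3: chance imbalance.** The standardized baseline difference between arms has SD sqrt(2/183) = 0.105. A 1.96-SD imbalance shifts the unadjusted log ratio by r × 2.197 × 1.96 × 0.105 = 0.450 × r (the baseline SD cancels). The GMT ratio is then multiplied by exp(0.450 × r): 1.05 at r = 0.1, 1.14 at r = 0.3 and 1.25 at r = 0.5. The unadjusted interval already allows for this on average; adjustment removes it.

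**Step 4: validity.** In 20,000 simulated trials with r = 0.5 and no true difference, the unadjusted one-sided test rejected in 2.4%, so the 2.5% level is kept.

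**PPS.** The documents give no exclusion rates, so no size can be computed.

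**The case against.** The strongest defence is that nothing is broken. Sample size and analysis use the same test, the stated power is reached and randomization protects the error rate. A reader might infer that the trial is underpowered or the test invalid; steps 1 and 4 show neither.

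The gain may also be small. Subjects are at least 6 months past their second dose and prior infection is an exclusion. Negative results are replaced by half the starting dilution (8.8.8). If many baseline values sit at that floor, r could be 0.1 to 0.2 and the gain only about 0.3 to 1.4 percentage points. This stands. A baseline BA.4/5 titer is also not explicitly promised, because 8.8.2 names no strain and 8.8.7 does not list its variants.

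Two further inferences are tempting. One is that centre belongs to the randomization structure; section 6.3.2 gives only a numbering rule, and no stratification or blocking by centre is stated. The other is that baseline and age are ignored altogether. They are not: the day-28 fold increase is a secondary endpoint, age-group tests are planned (8.11.2), and 8.11.4.3.3 stratifies variant GMTs by anti-Ad5 titer and age. None of these puts the pre-booster SARS-CoV-2 titer, age group or centre into the primary ratio.

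The SAP might add an adjusted model. However, the protocol itself names the t test, so this is a stated choice and not a detail left open. On the PPS, the FAS is already analysed, and most of the section 7.5 grounds concern eligibility or vaccination errors. That reduces the secondary point but does not remove it, since the PPS would still carry the claim.

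**Conclusion.** The point holds as an inexpensive improvement to a valid analysis. The unadjusted t test delivers the planned 85%. Adjustment would raise power at 183 per arm to between 85.7% and 96.4%, and narrow the interval by 0.5% to 20%, for r from 0.1 to 0.6. The power figures assume the plan's GMT ratio of 2 and log SD of ln 9, taken from pilot GMTs for which no strain is named. The size of the gain is uncertain because r is an assumption. Its direction is not in real doubt: with 366 evaluable subjects and a handful of covariates, adjustment costs almost nothing even when r is near zero.

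The preference for the FAS is a matter of principle for an open-label superiority comparison. A reader might infer that the PPS result will be biased in favour of the inhaled vaccine; the documents support neither a direction nor a size.

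**What to change.** In 8.11.2 and 8.11.4.3.1, make the primary analysis an ANCOVA of log10 day-28 titer with terms for arm, log10 pre-booster neutralizing titer, age group (18-59, 60 or over) and centre. Use the BA.4/5 baseline titer if it is assayed before the booster, otherwise the pre-booster neutralizing titer of 8.8.2, and state which in the protocol. Describe centre as a prognostic covariate, since stratification by it is not stated. Report the adjusted GMT ratio with its one-sided 97.5% lower limit against 1, and keep the t test as a sensitivity analysis.

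As a separate edit to 8.11.3, base the primary immunogenicity conclusion on the FAS, with the PPS supportive. Subjects without a day-28 titer still contribute no value there, so this reduces selection after randomization but does not abolish it.

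The main change needs no extra subjects or visits, and no extra assays if an existing baseline titer is used. It costs protocol and SAP wording, and the headline ratio becomes model-adjusted. The covariates should be fixed before any day-28 titers are seen, because adjustment chosen afterwards would carry little weight.

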8.11.5 Analysis plan

First-stage analysis:

The first analysis will be performed after the 28-day safety data have been reviewed.

Second-stage analysis:

The second analysis will be performed after the 28-day immunogenicity data have been reviewed.

Final analysis:

The final analysis will be performed after the 6-month safety and immunogenicity data have been reviewed.

8.11.6 Analysis software

SAS version 9.4 or above is utilized for analysis in this study.

9 CLINICAL TRIAL MONITORING

9.1 Responsibilities of the Parties

9.1.1 Investigator

The principal investigator is responsible for management and assignment of responsibilities for all personnel participating in the clinical trial.

The investigators shall keep the personal information of subjects confidential. Source records, eCRF, and other documents should only be identified by subject code and the randomization number. The investigators will save the identification list and screening registration forms of the subjects (including the full names, ages, and addresses) in the Investigator Site File. As per the GCP principles, the raw data of each subject is allowed to be monitored, audited, and reviewed.

9.1.2 Clinical research associate

The clinical research associate (CRA) shall perform the on-site follow-up monitoring regularly. During the monitoring, whether the raw data is consistent with the information on the eCRF will be verified, i.e., the accuracy and completion status. If the eCRF is found inconsistent with the raw data, it is necessary to urge the investigators to modify it. The CRA will evaluate the process of informed consent, the transportation and storage status of the investigational vaccine, the trial documents and the progress of the trial. The CRA will check the compliance of the investigators with the protocol (or protocol amendment), observe the procedures of the trial, and discuss the issues with the investigators. There should be monitoring records to document on-site monitoring.

9.2 Personnel Training

The trainees include site operators, laboratory operators, and clinical medical personnel. Training contents include study-related contents, study process, clinical techniques, and emergency handling.

9.2.1 Site operators

All the personnel participating in the clinical trial are investigators and are required to present medical/nursing professional qualification certificates (including medical practitioner certificate, and medical technician work license). Site operators are required to provide CVs (signed and dated) and relevant documents. These materials are filed in the training documents by the responsible person. All those participating in the training are required to register in the training registration form. A brief description of training topics or tasks shall be provided in the training meeting records, including reference from relevant documents, version number, and training date. Training shall be provided as appropriate by the responsible person when new staff are assigned to new posts. The training content shall be relevant to the (new) posts of the staff, and practical training is required.

9.2.2 Laboratory operators

Laboratory operators shall present qualifications above technician. Laboratory operators are allowed to perform laboratory operations only after they have received training in terms of the GCP, trial protocol, and SOPs, passed the examination, and been authorized by the principal investigator.

The contents of evaluation include:

- 1) quality of work;
- 2) mastery of new techniques and procedures;
- 3) observance of relevant technical instructions and procedures;
- 4) ability of appropriate explanation to results;
- 5) ability of error avoidance;
- 6) whether the test results meet the acceptance criteria defined in relevant documents;

Additional training must be performed in case new or modified testing processes or techniques are to be implemented.

9.2.3 Clinical medical personnel

Doctors are required to provide the identification of physician's qualification or medical practitioner certificate; nurses are required to provide the professional certificate of nursing; lab technicians are required to provide the work license.

Emergency doctors and nurses shall possess professional qualities, and techniques including cardiopulmonary resuscitation, shall be currently engaged in emergency work and acquainted with the emergency treatment for common vaccination adverse reactions, especially immediate hypersensitivity reaction, and be acquainted with the process of emergency green channel.

The principal investigator or CRA should provide training for each medical personnel related to each function. Refer to the GCP and "Field Operations Manual".

